5.0 REGISTRATION PROCEDURES

Approximately 32 subjects will be enrolled onto this study; four to eight individuals will be assigned to one of four different categories for comparisons to be made; an additional series of 12 patients will be enrolled in groups of 4 and assigned to three different categories. Patients can be registered only after the eligibility criteria are met. In addition, the following information must be provided:

- Patient's name and ID number.
- Verifying Physician's Name.
- Demographic Data.
- Treatment planning and start date.
- Eligibility criteria information.
- Patient's consent to enroll in the study
- All eligibility source documentation and checklist will be sent to the CTU QA office for review prior to subject enrollment

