6.0 RADIATION THERAPY

Patient will have a treatment planning session for delivery of radiosurgical treatments and an immobilization device will be custom made for every patient, per standard of care. Specification of patient immobilization for each radiation treatment will conform to institutional practice.

Serum Blood Markers:

Patients will be asked to participate in ELISA blood testing just prior to and immediately following each daily radiation therapy session. Approximately 5cc of blood will be collected

within 2 hours prior to and following completion of fractionated radiation therapy to assess the levels of MIF (both MIF-1 and MIF-2) and VEGF. This whole blood will be separated into plasma and rapidly frozen at -80 C using standard procedures. At later time points, plasma samples will be thawed and subjected to an ELISA for each of the markers using commercial kits and standards. Given that survival or regrowth of tumor vasculature has been suggested to be a major determinant of radiation responses, measurement of VEGF levels prior and following radiation, these tests may give a predictive indication of tumor response.

Pending patient approval, we will also store remaining plasma samples for detection of additional cancer markers to potentially improve our ability to predict for response to therapy with new tumor markers.

Radiation Doses:

Radiation will be delivered in 4 fractions. The initial dose level will be 6 Gy per fraction to a total dose of 24 Gy in 4 fractions. Doses will be escalated at 2 Gy per fraction increments to 12 Gy per fraction to a total dose of 48 Gy. The radiation treatment planning and evaluation details are appended.

Series I:

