Twenty patients who are not surgical candidates will be offered treatment with a radio-surgical technique. Four patients will be registered in each dose group. Treatments will be initiated with 4 patients utilizing the minimum dose and observe what happens. If no DLTs are observed, then escalation to the next set of 4 patients to the next initial dose level will occur. If 1 DLT is observed, treatment of the next set of 4 patients at the same dose level will occur. If zero or 1 additional DLTs are observed, then dose escalation occurs as previously described. However, if $\geq 2/4$ or $\geq 3/8$ are observed at a given dose level the trial stops. On average, this results in between 4-5 patients being treated before escalation. The table below shows the probability of stopping giving an underlying toxicity level using this design.

Table: Probability of stopping escalation given underlying toxicity

Underlying Pr(Toxicity)	0.1	0.2	0.25	0.3	0.35	0.4	0.5	0.6	0.7	0.8	0.9
Pr(Stopping)	0.07	0.25	0.37	0.49	0.61	0.71	0.86	0.95	0.99	0.998	0.999

If a patient fails original treatment, he or she will be either kept on study for observation, or if they require retreatment, they will be taken off study.

Series II

The next series will be reached if insufficient dose limiting toxicities have occurred upon completion of the initial dose escalation series I to a total dose of 48 Gy in 4 fractions to warrant limitation of further dose escalation.

At this level, if normal tissue toxicities for SBRT have not proven to be problematic for renal lesions, then “standard” dose and fractionations will be prescribed for subsequent patients as would be used for example in Lung cancer. Given the 90% expectant local control for lung

lesions given 20 Gy in 3 fractions, we are highly anticipating reaching an efficacious dose during series II of the trial. If the 12 Gy x 4 fraction cohort is irradiated without dose limiting toxicities, then 12 additional patients will be accrued for further dose escalation following dose toxicity criteria defined below:

Based on the Linear Quadratic Model commonly used for radiobiologic comparisons, each subsequent group of four participants will receive further dose escalation using a 3 fraction regimen to increase beyond 48 Gy in 4 fractions in 20% dose equivalent increments.

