9.0 STATISTICS

Statistical Considerations

The primary goal of this study is to compare and evaluate toxicities across four varied treatment schemes using a dose escalation design with four cohorts of 4-8 patients each. Escalation to the next dose will take place if no DLT's are observed in the first four patients treated at the current dose. If 2 or more DLT's are observed in the first four patients, then escalation is stopped. If 1 DLT is observed, then four more patients are treated at the same dose, and dose escalation stops if 2 or more of these next four (3/8 of patients treated at that dose) experience a DLT. If the probability of a DLT is 40%, there is a 71% chance of stopping at the current dose, whereas if the probability of DLT is 10%, there is only a 7% chance of stopping the dose escalation.

All analyses of the data will be descriptive. Clinical and radiographic efficacy will be summarized by calculating Kaplan-Meier curves for the following: overall survival, disease-free

survival, time to local progression, time to distant failure. Data from all dose groups will be pooled in these analyses. Survival rates estimated from the Kaplan-Meier curves will be estimated with 95% confidence intervals. Rates of acute and late side effects and adverse events will be summarized as proportions, with 95% confidence intervals.

Sample Size

The number of patients studied in this trial is determined by the dose escalation strategy and the number of DLT's that are observed at each dose level. With four dose levels and cohorts of 4-8 subjects per dose, the minimum sample size is 2 and the maximum is 32. It is expected that around 20 subjects will be enrolled. This design with cohort sizes of 4-8 per dose ensures that the probability of escalating to the next dose is .93 when the probability of DLT is .1, but is only .05 when the probability of a DLT is .6.

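### The stated sample size for the trial (2 to 32, about 20 expected) covers Series I only: the 12 Series II patients raise the maximum to 44 (or 40), and the design gives a minimum of 4, not 2

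*Combined protocol and SAP*

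**What the plan says.** Section 9 (Sample Size) says that the escalation strategy determines the number of patients in the trial, and gives: "With four dose levels and cohorts of 4-8 subjects per dose, the minimum sample size is 2 and the maximum is 32". It expects around 20. The design it describes is "using a dose escalation design with four cohorts of 4-8 patients each".

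The rules in Section 9 are judged on complete groups of four. On moving up, it says: "Escalation to the next dose will take place if no DLT's are observed in the first four patients treated at the current dose". The stopping side of the rule looks at the same group of four and reads: "If 2 or more DLT's are observed in the first four patients, then escalation is stopped". With exactly one DLT, a second group of four is treated at that level, and two or more DLTs in the second group end escalation.

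Section 6 sets the Series I levels, starting at 6 Gy per fraction: "Doses will be escalated at 2 Gy per fraction increments to 12 Gy per fraction to a total dose of 48 Gy". It speaks of twenty patients in Series I, says "Four patients will be registered in each dose group", and adds: "On average, this results in between 4-5 patients being treated before escalation". It then describes Series II: 12 further patients, in successive groups of four at three higher levels.

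Section 5 puts total enrolment at approximately 32. The same sentence mentions four categories of four to eight patients and says that "an additional series of 12 patients will be enrolled in groups of 4 and assigned to three different categories".

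**The concern.** Section 9 describes four levels, whereas Sections 5 and 6 describe up to seven. A maximum that leaves out three planned groups is not the maximum for the trial. A trial that follows its own rules could pass it without any deviation.

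The number 32 also appears twice with different meanings. In Section 9 it is a ceiling for Series I. In Section 5 it is an approximate total in a sentence that includes Series II. Because the two agree, the omission is easy to miss, and a reader cannot tell which figure limits accrual.

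The minimum of 2 conflicts with the cohort size in its own sentence. At stake are the planned number of exposed patients and the accrual ceiling. No power calculation is affected, because the analyses are descriptive.

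**Working it through.** **Inputs.** Series I levels are 6, 8, 10 and 12 Gy per fraction, so four (Section 6). Each level takes 4 patients, expandable to 8 (Sections 6 and 9). Series II is three groups of 4, 12 in all (Sections 5 and 6). The documents give no DLT rate for the expected figures, so I assume a constant rate p per level and vary it. I also assume that all 12 Series II patients are accrued once that series opens.

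**1. The plan's own figures.** Let P0, P1 and P2+ be the binomial probabilities of 0, 1 and at least 2 DLTs in four patients.
- P(stop at a level) = P2+ × (1 + P1).
- At p = 0.10: P0 = 0.6561, P1 = 0.2916, P2+ = 0.0523. P(stop) = 0.0523 × 1.2916 = 0.068; the plan says 0.07.
- At p = 0.40 the result is 0.706; the plan says 0.71. All 11 entries of the stopping table reproduce within two points.
- Series I maximum = 4 × 8 = 32, as stated.

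**2. Minimum.** The smallest trial stops after at least two DLTs in the first group, which is 4 patients. A minimum of 2 needs accrual to halt inside a cohort when the first two patients both have a DLT. No such rule is written.

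**3. Whole-trial maximum.** Section 6 states the condition for Series II twice. One sentence opens it if Series I ends with too few DLTs to limit further escalation (the looser condition). Another opens it if the 12 Gy × 4 cohort has no DLT (the stricter condition).
- Looser condition: 32 + 12 = 44, which is 37.5% above 32.
- Stricter condition: the last Series I level cannot have expanded, so 3 × 8 + 4 + 12 = 40, which is 25% above 32.
- A trial completing both series treats at least 16 + 12 = 28.

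**4. Expected numbers.** Patients per level: E[n] = 4 + 4 × P1. Series I: E[N] = E[n] × (1 + e + e² + e³), with e = 1 − P(stop). Whole trial: add 12 × P(Series II opens). That probability is e⁴ under the looser condition and e³ × P0 under the stricter one.

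| p | E[n] per level | Series I E[N] | P(opens), looser / stricter | Whole trial, looser / stricter |
|---|---|---|---|---|
| 0.05 | 4.69 | 18.29 | 0.936 / 0.775 | 29.52 / 27.59 |
| 0.10 | 5.17 | 18.66 | 0.756 / 0.532 | 27.74 / 25.05 |
| 0.20 | 5.64 | 15.30 | 0.308 / 0.169 | 19.00 / 17.34 |

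For example, at p = 0.10 under the looser condition, 18.66 + 12 × 0.756 = 27.7.

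**5. Chance of passing 32.** If k Series I levels expand and Series II opens, the total is 16 + 4k + 12, which exceeds 32 when k is at least 2. The probability at p = 0.05, 0.10 and 0.20 is 0.13, 0.26 and 0.19 under the looser condition, and 0.06, 0.11 and 0.07 under the stricter one.

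**6. Section 5 and Section 6 totals.** Section 5's approximate 32 equals 20 + 12, which appears to be its origin. Section 6's four per group over four levels is 16, not 20. The 20 makes sense only as an expectation that allows for expanded cohorts.

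**The case against.** The strongest reply is that Section 9 names its scope, four dose levels, and that 4 × 8 = 32 is right for it. That stands: the maximum is a fault of scope, not of arithmetic. But the section presents the figure as the size of the trial and does not send the reader to Series II.

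It can also be said that Section 5 already counts Series II, as 20 + 12. That is the likely reading. It makes the Section 5 figure an approximate total and the Section 9 figure a ceiling for one series, so it explains the coincidence without removing the need to reconcile them.

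A reader might infer three stronger criticisms, which the documents do not support:
- *That the maximum is 56 (7 × 8).* This needs the expansion rule to apply in Series II. No section says so; Sections 5 and 6 fix Series II at three groups of four.
- *That the expected 20 cannot be reproduced.* For Series I it is close: 18.7 at a 10% rate, and up to about 19.5 when the rate rises across levels. With a constant rate it is within two patients of 20 for rates of about 4% to 13%.
- *That the average of 4 to 5 patients before escalation is wrong.* It holds at DLT rates up to about 8%. Averaged over all outcomes at a level, it is exceeded by at most 0.7 patient (5.69 at 25%). It lacks a stated rate, which is a minor matter.

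Finally, DLT rules rather than a ceiling drive Series I, and no precision target depends on N. That limits the consequence but does not make the stated range correct.

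**Conclusion.** The point holds as one of scope and counting. The Section 9 range of 2 to 32, with about 20 expected, describes Series I alone, and its lower end is wrong for cohorts of four. For the whole trial the range is 4 to 44, or 4 to 40 under the stricter wording of the Series II condition. The understatement of the maximum is 8 to 12 patients.

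The maxima and the minimum are pure counts and need no assumed DLT rate. They rest on Series II groups staying at four and on no halt within a cohort. The expected totals, about 25 to 30 for the whole trial at DLT rates of 5% to 10%, rest on the constant-rate assumption and on full accrual of Series II once open. The two wordings of the Series II condition must be reconciled; this review does not say which is right.

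**What to change.** State one set of figures in Sections 5, 6 and 9, labelled by series:
- Series I: minimum 4, maximum 32. If the sponsor intends accrual to halt within a cohort once two DLTs occur, state that rule and keep 2.
- Label the expected 20 or so as the Series I expectation at low DLT rates (about 18 to 19 at 5% to 10% per level). In Section 6, say that four per group is the initial cohort size, so that it no longer reads as 16 against 20.
- Whole trial: maximum 44, or 40 under the stricter condition, once the two wordings in Section 6 are reconciled; expectation about 25 to 30 at DLT rates of 5% to 10%.
- Section 5: say whether the approximate 32 is an expected total including Series II.
- Optionally, tie the 4 to 5 patients before escalation to a DLT rate of about 8% or less, noting 5.2 at 10% and 5.6 at 20%.

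The cost is wording in three sections. The stated accrual ceiling rises by 8 to 12 patients; the design does not change.

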10.0 COSTS AND COMPENSATION

The costs of procedures, tests, visits and hospitalizations in connection with the radiosurgery treatments are standard of care and will be billed to the subject's insurer and/or to the subject (regardless of which group the subject is placed into). Costs for pre-treatment diagnostic scans, radiation therapy treatments, and post-operative follow-up are also standard of care and will be charged accordingly. Therefore, subjects and their insurers will be fully responsible for the costs related to this research evaluating and comparing standard of care procedures. Subjects will not be paid for their participation in this study.

11.0 RISKS

Risks include those that result from the special nature of radiosurgery standard of care, including errors in giving the radiation. This may include giving radiation to normal tissue around the tumor and not to the cancer, or giving the wrong dose of radiation, either too much or too little. Any of these problems could potentially be severe, possibly even fatal. There may be risks from assigning a subject to one of the four research categories versus any one of the other three options. The research physician cannot pre-determine which category is best for any individual patient as a purpose of this study is to evaluate and compare the four options.

The use of radiation in any form is also associated with a small risk of causing another cancer, either in the portion of the body directly exposed to radiation during treatment (the target of treatment), or in other sites of the body due to low doses of scattered radiation. Depending on which category a subject is assigned, the risk may be greater or smaller for one subject than for others in the study.

Because radiosurgery for treating a kidney tumor is a very new approach, there may be other risks that we are not yet aware of, some of which could potentially be severe.

All data entered into the computer will be coded and personal identifiers will be removed. All data that can be linked to an individual will be protected and the master list will be stored off-line

and will be available only to the principal investigator or his or her designee(s). Although every effort will be made to protect and maintain confidentiality, there is a slight risk of loss of confidentiality.

12.0 DATA SAFETY AND MONITORING

Clinical information from subjects will be recorded onto Case Report Forms and subsequently transferred into OnCore. Patients who additionally consent to a separate Urology Registry will have their data added to the Urologic Oncology & Minimally Invasive Therapies Database for UHHS Faculty (UHCMC IRB No. DBR0006-CC031).

Should any unanticipated adverse device events occur during the course of the study, the clinical research coordinator will ensure that they are documented by the investigator and reported to the University Hospitals Cleveland Medical Center Institutional Review Board (UHCMC IRB) per its then-current guidelines. An unanticipated adverse event is defined by the FDA as any serious adverse effect on health or safety or any life-threatening problem or death caused by, or associated with, a device, if that effect, problem, or death was not previously identified in nature, severity, or degree of incidence in the protocol (including a supplementary plan), or any other unanticipated serious problem with a device that relates to the rights, safety, or welfare of subjects. If the determination is made that an unanticipated adverse event presents an unreasonable risk to subjects, the clinical evaluation will be paused, or if deemed appropriate (to enable further investigation), the subject will be withdrawn as soon as safely possible.

Adverse events, grade 2 and above, will be captured in OnCore and will be reported in accordance with the Data and Safety Monitoring Plan (DSMP) that is approved by the Cancer Center Protocol Review and Monitoring Committee (and aligned with the NCI-approved plan). All monitoring and reporting will be compliant with policies presented in the most current version of the CCCC Clinical Trials Operations Manual, so that an independent assessment can be made of study activities. The study will be updated to remain compliant with any changing rules/policies of the CCCC.

All serious adverse events (SAE's), and IRB continuing renewals including review of toxicity will be promptly submitted to the University Hospitals Cleveland Medical Center IRB.

Tumor measurements will be defined by the principal investigator or treating physician and confirmed by a radiation oncologist or radiologist not associated with this study. In addition, responses will be reported directly to the CCCC Data Safety and Toxicity Committee (DSTC) for confirmation of objective responses reported. Submissions will be made within accordance with reporting timelines. The study PI, co-investigators, and/or research staff will monitor all patients on the trial, and will evaluate patients at each treatment encounter and in follow-up. Serious adverse events are reported to the attending physician, the Principal investigator (PI), the DSTC, and the UHCMC IRB per IRB guidelines.

Accessing Electronic Medical Records

This study will access both paper and electronic medical records systems to obtain medical information for the subjects. Therefore, electronic medical records must be utilized to obtain medical information in a timely manner. The names will come from surgeon's offices (staff and records), tumor boards, surgical schedules, IDX and the surgeon's direct referral. Each patient will be approved by the surgeon before contact by the research individual occurs. Physician Portal, EMR and paper charts will be used to screen for eligibility. Paper copies of the eligibility criteria (pathology reports, laboratory results, etc.) will be kept in the shadow charts by the study coordinator. The shadow charts will be kept in a secure, locked area. Clinical data will be tracked in Oncore. Other data, such as treatment planning images, will be maintained on a password protected computer located in the Department of Radiation Oncology on a secured server.

Response Criteria

Response will be assessed using tumor measurements (longest dimension) obtained from MRI and/or CT with or without contrast, documentation of presence of metastatic disease, results of post-treatment pathology (if available).

Definitions of response:

- Stable – no change
- Progressive Disease – 20% or more increase in sum of diameters of the target lesion. The sum must also demonstrate an absolute increase of 5 mm or more or the presence of a new lesion or lesions.
- Partial Response - At least a 30% decrease in the sum of diameters of target lesions, taking as reference the baseline sum of diameters.
- Complete Response – no visible target lesions
- Pathological Complete Response – Based on increase or decrease of available biopsy results

Appendix I.

It is important to note that dose to the normal tissues surrounding the target has not been allowed to dose escalate. Tolerance levels selected for these normal organs (see Table I. and Appendix I., are consistent with RTOG standards and normal tissue limits approved for UHCMC Protocol Case 13807 associated with Prostate Cancer with Cyberknife irradiation.

Table I. Dose Specifications for Normal Organs (and Appendix I.)

6. Bowel – No more than 1 cc can receive 8 Gy/fx for a total of 24 Gy in 3 to 4 fractions.
7. Cord – No more than 0.3 cc can receive 6.7 Gy/fx for a total of 20 Gy in 3 to 4 fractions.
8. Stomach - No more than 1.0 cc can receive 7.3 Gy/fx for a total of 22 Gy in 3 to 4 fractions.
9. Liver – No more than 2/3 of liver volume can receive 5.7 Gy/fx for a total of 17 Gy in 3 to 4 fractions. Additionally within that volume – 800 cc should not receive more than 5.0 Gy/fx for a total of 15 Gy in 3 to 4 fractions.
10. Contralateral Kidney- No more than 5 % of the volume can receive more than 4.7 Gy/fx for a total of 14 Gy in 3 to 4 fractions.
